4.10.3 Deaths, Serious Adverse Events, and Other Significant Adverse Events

The following summaries will be provided:

- A summary of the number and percentage of participants reporting a treatment-emergent AE with outcome of death by treatment group, SOC and PT
- A summary of key participant information for participants reporting treatment-emergent AE with outcome of death
- A summary of the number of SAEs reported by treatment group, SOC and PT
- A summary of the number and percentage of participants reporting a SAE by treatment group, SOC and PT
- A summary of key participant information for participants reporting a SAE

The number and percentage of participants reporting a treatment-emergent AE leading to death, and SAEs by treatment group, SOC and PT will also be presented for the Monotherapy Safety Analysis Set and the Extended Safety Analysis Set with Week 12 flag.

4.10.4 Clinical Laboratory Evaluation

The following summaries will be provided:

- A summary of the observed absolute values and change from baseline in each haematology and clinical chemistry laboratory parameter by treatment group and time point.
- A summary of baseline versus maximum observation on treatment in each laboratory parameter by treatment group (shift table)
- A summary of baseline versus minimum observation on treatment in each laboratory parameter by treatment group (shift table)
- A summary of key participant information for participants reporting changes outside reference ranges in each laboratory parameter
- A summary of the number and percentage of participants reporting changes outside reference ranges in each laboratory parameter
- A plot of alanine aminotransferase (ALT) versus total bilirubin, expressed as multiples of upper limit of normal (ULN)
- A plot of aspartate aminotransferase (AST) versus total bilirubin, expressed as multiples of ULN
- A plot of liver biochemistry over time, for participants with potential Drug Induced Liver Injury (ie, $ALT/AST \geq 3 \times ULN$ and total bilirubin (BILI) $\geq 2 \times ULN$, and in which the elevation in transaminases precede or coincide with (that is, on the same day as) the elevation in BILI or $ALT/AST \geq 5 \times ULN$)
- A summary of the number and percentage of participants reporting maximum on-treatment ALT and AST by maximum total bilirubin for assessing Hy's Law criteria
- A summary of individual participant data for participants with Potential Hy's Law ie, participants with combined ALT or AST, and bilirubin elevations
- A summary of treatment-emergent laboratory changes will be presented for the Safety Analysis Set, the Monotherapy Safety Analysis Set (Treatment Period 1) and the Extended Safety Analysis Set with Week 12 flag (Treatment Period 2).

Treatment-emergent laboratory and vitals change (TELVC) limits of interest for this study are provided in [Appendix C](#) for the laboratory parameters, and in [Table 5](#) for vital signs.

By-participant listings of all laboratory data will be provided including participant identifier, treatment, age, sex, race, visit, category, laboratory test name, result, and standard units. Laboratory reference ranges will also be listed and out of range values will be flagged.

4.10.5 Vital Signs, Physical Findings and Other Observations Related to Safety

ECG measurements will be evaluated by the clinician at each visit described in the SoA in [Appendix A](#) as either normal or abnormal. Number and percentage of participants with normal and abnormal ECG readings by visit will be presented by treatment group. Abnormal ECG results and reasons entered into the CRF will be listed by participant and by visit.

Potentially clinically significant (PCS) ECG values will be identified from Third Party Vendor data collected. The predefined criteria (based on severity) for PCS ECG values are displayed in [Table 4](#).

Table 4 Potentially Clinically Significant ECG Predefined Criteria

Variable	Unit	Outside lower limit if	Outside upper limit if	AZ extended reference range - low	AZ extended reference range - high	Treatment emergent increase if	Extended treatment emergent increase if
Heart rate	bpm	< 50	> 100	< 45	> 120	NA	NA
				< 30	> 150		
RR interval	ms	< 600	> 1200	< 500	> 1333	NA	NA
				< 400	> 2000		
PR interval	ms	< 110	> 220	< 100	> 240	> 40	> 60
QRS	ms	< 75	> 115	< 70	> 120	> 15	> 30
QT	ms	< 320	> 450	< 300	> 480	> 30	> 60
					> 500		
QTcF	ms	< 320	> 450*	< 300	> 480*	> 30*	> 60*
					> 500*		
QTcB	ms	< 320	> 450*	< 300	> 480*	> 30*	> 60*
					> 500*		

* Cut-off values for categorical analyses as recommended by ICH E14 (Note, more than one category for high range increases in QT/QTc values)

Note, lower and upper RR interval limits and low and high RR interval reference ranges (all in ms), represent respectively the upper and lower heart rate limits and high and low heart rate reference ranges (all in bpm)

Note, no standard criteria are established for treatment emergent increases or decreases in RR intervals or heart rates, or for treatment emergent decreases in PR, QRS or QT/QTc intervals

ms = milliseconds, bpm = beats per minute: NA= not applicable.

Notable changes from pre-dose at each post-dose time point for vital sign parameters will be identified. The predefined criteria for notable changes in vital signs values are displayed in [Table 5](#).

Table 5 Vital Sign Notable Change Predefined Criteria

Vital sign		Observed value	Notable change from baseline
Systolic BP (mmHg)	High	≥ 140	Increase of ≥ 20

	Low	< 90	Decrease of ≥ 20
Diastolic BP (mmHg)	High	≥ 90	Increase of ≥ 10
	Low	< 60	Decrease of ≥ 10
Pulse Rate (bpm)	High	≥ 110	Increase of ≥ 20
	Low	< 50	Decrease of ≥ 20
Pulse Oximetry	High	N/A	N/A
	Low	< 90%	Decrease of $\geq 5\%$

BP = blood pressure.

For by-visit summaries, the last non-missing assessment (including repeat assessments) recorded at each applicable scheduled visit will be summarised.

The following summaries will be provided:

- A summary of the observed absolute values and change from baseline in each vital sign parameter by treatment group and time point.
- A summary of key participant information for participants reporting notable changes outside predefined criteria in each vital sign parameter.
- A summary of the number and percentage of participants experiencing notable changes from baseline outside predefined criteria, by vital sign parameter and treatment group.
- A summary of the observed absolute values and change from baseline in each ECG parameter by treatment group and time point. Both pre- and post-investigational medicinal product (IMP) measurements will be presented at each time point.
- A summary of the number and percentage of participants with QTcF intervals exceeding predefined upper limits (as stated in [Table 4](#)).
- A summary of ECG assessment (normal/abnormal [clinically significant, not clinically significant]), baseline versus last observation on treatment. Post-IMP measurement at last observation on treatment will be used.
- A summary of key participant information for participants reporting PCS ECG values outside predefined criteria by treatment group and visit.
- A summary of the number and percentage of participants reporting PCS ECG values outside predefined criteria, by ECG parameter and treatment group.

By-participant listings of vital sign parameters, abnormal ECG results, and weight, height, and BMI will also be provided.

Any new or aggravated clinically relevant abnormal medical finding at a physical examination as compared with the baseline assessment will be reported as an AE unless unequivocally related to the disease under study.

4.10.6 Safety Monitoring

This is not applicable for this study.

4.11 Other Analyses

4.11.1 Pharmacokinetics

Following the early termination of the FLAIR study, it was confirmed that all PK analysis (AZD5718 and Dapagliflozin) is no longer required for Final Analysis.

4.11.2 Retinal Sub-Study

The retinal study to be performed on eligible DKD study participants will provide descriptive summaries of BCVA and OCT, as described in Section 3.2.3.1. Summary statistics and change from

baseline will be presented by visit for each treatment group. The baseline assessment is taken during screening.

Cataract assessments will be presented by visit for each treatment group.

By-participant listings of **CCI** and **CCI** measurements will be presented by treatment group and visit for DKD participants only.

4.12 Interim Analysis

An administrative interim analysis will be performed for this study when approximately 211 participants have reached Week 20. A separate review committee of AstraZeneca representatives will review the unblinded interim outputs. The design and the conduct of the study will not be impacted by the results observed at the interim. The main study team will remain blinded for the duration of the study.

The blinding maintenance plan (BMP) will document study roles which have access and will receive unblinding study data. Unblinded data will be received for the interim analysis and following unblinding for DBL. A separate unblinded study team will be implemented at Parexel to run and deliver unblinded outputs to a separate independent unblinded team at AstraZeneca. Further detail of the logistics of the interim within AstraZeneca are included in the interim analysis charter, which will be stored in the AstraZeneca eTMF.

The interim analysis will be performed on clean data, such that the data for the participants included in the interim analysis will be cleaned and fully coded, where appropriate. The outputs for the interim analysis will be a subset of the outputs for the primary analysis. These will be clearly marked in the mock shells. Further details are provided in [Appendix B](#).

4.12.1 Early Termination of Study

Following the results observed at the interim analysis, it was confirmed by sponsor to terminate the study due to lack of efficacy. There were no safety concerns related to the study. All participants who were on-going in the study were allocated early termination visits. The main study team remained blinded to treatment allocation for the final analysis. Details of changes to planned analysis from those outlined in the protocol are highlighted in Section 4.14. This includes the removal of MCP-Mod analysis, and all PK analysis from the final analysis.

4.13 Determination of Sample Size

For the primary endpoint, a total of 142 evaluable participants per group will provide **CCI** power to detect a placebo-adjusted **CCI** reduction in urine ACR from baseline between AZD5718 **CCI** mg and placebo group with **CCI**, assuming a SD of **CCI** on the natural log-scale. It will also assure at least **CCI** power to detect the same urine ACR reduction and the significance of dose-response over multiple dose-response models in the DKD sub-population. To account for approximately **CCI** discontinuation, 158 participants per group will be enrolled.

The sample size was calculated using nQuery (version 8.2.0.0) and validated using EAST (version 6.4.1).

4.14 Changes in the Conduct of the Study or Planned Analysis

Following the results from the interim analysis, it was decided to terminate the study early and reduce the scope of analysis. This decision led to the removal of the MCP-Mod analysis as outlined in the protocol, and the previously described sensitivity analysis for the ABPM analysis. The statistical analysis plan has been updated to include only the analysis which will be performed following database lock.

Pharmacokinetic analyses of AZD5718 and dapagliflozin were also removed from the final analysis. The statistical analysis plan has been updated to reflect this.

Due to the early termination of the study, the total number of randomised participants is 613 with 340 participants completing treatment. Therefore, efficacy analyses should be evaluated with caution due to lack of power.

The total study duration, as highlighted in Section 3.1, will vary following study termination, up to a maximum of 28 weeks.

6 APPENDIX

Parexel International

AstraZeneca

Statistical Analysis Plan

Appendix A: Schedule of Activities

Table 6 Schedule of Activities

Study Period	Screening		Treatment Period 1				Treatment Period 2			Discontinuation	Follow-up
	1	2	3	4	5	6	7	8	9		10
Visit Number											
Study Day	-32 to -3		1	15±3	29±3	57±3	85±3	113±3	141±3		169±5
Study Week	-4 to 0		1	2	4	8	12	16	20		24
Informed consent (main)	X										
Informed consent (optional) for genetic and biomarker research	X										
Verify eligibility criteria	X	X	X				X ^a				
Demography	X										
Full physical examination including height, weight and BMI	X ^b		X		X		X		X	X	X
Physical examination (abbreviated)				X		X					
Medical history	X										
Serum hCG, FSH and LH ^e	X										
Pregnancy test ^c			X								
Drug and alcohol screen	X										
Hepatitis B and C screening	X										
Spot urine for ACR	X										
Safety laboratory assessments (Clinical chemistry, haematology, coagulation, urinalysis) ^d	X		X ^e	X	X	X	X	X	X ^e	X ^e	X
12-lead ECG	X		X	X	X	X	X	X	X	X	X
Vital signs ^f	X		X	X	X	X	X	X	X	X	X
Randomisation			X								
Retinal study (optional DKD sub-group only) ^g	X						X				
HbA1c ^h	X								X		
Calculation of eGFR	X		X	X	X	X	X	X	X	X	X
Blood sample for cystatin-C	X		X	X	X	X	X	X	X	X	X

Parexel International

AstraZeneca

Statistical Analysis Plan

Study Period	Screening		Treatment Period 1				Treatment Period 2			Discontinuation	Follow-up
	1	2	3	4	5	6	7	8	9		10
Visit Number	1	2	3	4	5	6	7	8	9		10
Study Day	-32 to -3		1	15±3	29±3	57±3	85±3	113±3	141±3		169±5
Study Week	-4 to 0		1	2	4	8	12	16	20		24
Pharmacokinetics plasma sample for AZD5718				X (pre-dose)	X ⁱ (pre-dose)	X (pre-dose)	X (pre-dose)	X (pre-dose)	X (pre-dose)	X (pre-dose)	
Pharmacokinetics plasma sample for dapagliflozin								X (pre-dose)	X (pre-dose)		
CCI [REDACTED]		X	X		X		X		X		
CCI [REDACTED]			X		X		X	X	X	X	
Plasma, serum, and urine for future use (optional) ^{j, h}			X		X		X		X	X	
Blood sample for genomic initiative (optional) ^j			X								
Dispense supply of containers for urine samples	X	X	X	X	X	X	X	X	X		
E-Diary, dispensation and completion of diary ^k			X	X	X	X	X	X	X	X	X
Reminder to collect first morning void urine samples, 3 days before visit ^l	X	X	X	X	X	X	X	X	X	X	
Urine samples for ACR ^{h, m}		X	X	X	X	X	X	X	X	X	X
24-hour ABPM, provision and completion		X ⁿ	X ^o			X ⁿ	X ^o				
Study drug dispensation ^p			X		X	X	X	X			
Study drug returned ^{p, q, r}					X	X	X	X	X	X	
Study drug intake in study centre			X	X	X	X	X	X	X	X	
Assessment of AEs/SAEs	Only SAEs		X	X	X	X	X	X	X	X	X
Concomitant medications	X	X	X	X	X	X	X	X	X	X	X

- a Any participant with urine ACR < 30 mg/g at Week 12 will be excluded from Treatment Period 2. The eligibility check to enter Treatment Period 2 will be done at Visit 7 (Week 12) using the last available urine ACR result, calculated as the geometric mean of the replicated measurements using 3 sequential first morning urine voids.
- b Full physical examination will be completed at the indicated visits, with the exception that height will only be recorded at Screening Visit 1.
- c Serum hCG, FSH, and LH tests, and a urine dipstick pregnancy test are required for all women.
- d Except for Screening Visit 1, participants should be requested to be in a fasting state (except water) for at least 8 hours prior to sample collection and samples should be collected in the morning.

Parexel International

AstraZeneca

Statistical Analysis Plan

- e To include thyroid function tests (TSH, fT4 and fT3).
- f All vital signs (blood pressure, heart rate, respiratory rate, body temperature and pulse oximetry) will be measured with the participant in a supine position having rested for at least 10 minutes before each reading and should be taken before any blood draws. Vital signs should be collected pre-dose on the days of study drug dosing.
- g Optional, to be conducted only at study centres with the appropriate facility to conduct the assessment. There is no requirement for all participants at centres undertaking the sub-study to participate.
- h To be collected prior to study drug administration.
- h Containers to be dispensed at any study visit as required.
- i At specific PK sampling sites, for a sub-group of at least 80 participants (20 per dose group including placebo), 4 additional PK samples will be collected at this visit within 1-2 h, 2-5 h, 5-8 h, and 8-12 h post-dose. Pre-dose samples will be collected for all participants. Each PK sample must be separated by at least 1 h.
- j Only if consent is obtained. The blood sample for Genomic Initiative will be obtained from the participants at Visit 3 prior to study drug administration (at or after randomisation). If for any reason the sample is not drawn at Visit 3, it may be taken at any visit window until the last study visit. Only 1 sample should be collected per participant.
- k Participants will be requested to download an e-Diary application on their smartphones starting from Visit 3, in order to set study reminders and capture drug accountability throughout the treatment period, at sites where applicable. If needed, participants may be provided with a smartphone in order to use the application. Participants will be trained on how to use the application/device and the site will help the participants to login into the application for the first time. Data will be available to the site/Sponsor in real time. The participants who received a smartphone to use the e-Diary will return the smartphones at the last visit. Prior to deleting the e-Diary application from their personal smartphone, or returning a site provided smartphone, the participants will be requested to complete a satisfaction survey through the application (this survey is only applicable for e-Diary). When completion of an e-Diary is not applicable, participant will be requested to complete a paper dosing diary.
- l Phone call will occur after results from Screening Visit 1 are available and the participant is confirmed eligible in order to remind the participant to collect the first morning void urine samples and schedule the Screening Visit 2. If scheduled Visit 3 (Week 1) or Visit 7 (Week 12) will need to be delayed due to the need to repeat ABPM recording there is no need to repeat collection of the 3 urine samples.
- m Participants to collect first morning void urine samples on 3 consecutive dates (ideally day of visit and each of the preceding 2 days [refrigerated overnight] which are returned on the day of visit). This collection may be repeated once during the course of screening.
- n Participants will be provided an ABPM cuff at Screening Visit 2 and Visit 6 (Week 8) and instructed to perform ABPM 24-hours before their next visit ie, Visit 3 (Week 1) and Visit 7 (Week 12), respectively. Site will be asked to call the participant the day prior to next visit as a reminder to complete assessments. The participant may also visit the site for ABPM cuff placement 1 day before their next visit of scheduled assessment (i.e., Visit 3 [Week 1] and Visit 7 [Week 12], respectively)
- o Sites should ensure that the validity criterion described in Section 8.2.5 (CSP) is met prior to completing any other assessments at the visit. If the validity criterion is not met, the associated study visit may be rescheduled to allow for a repeat ABPM recording only if the rescheduled visit can be completed within the specified tolerance period for study visits:
- Visit 3: up to 72 hours following the originally scheduled visit for Visit 3 but no more than 32 days from Screening Visit 1.
 - Visit 7: ± 72 hours from Day 85.
- If a repeat ABPM session is not possible, the study visit should proceed as indicated. In addition, the visit should also continue if the ABPM session does not meet the validity criterion after the repeat session.
- p Study drugs refer to AZD5718/placebo during Treatment Period 1 and AZD5718/placebo + dapagliflozin during Treatment Period 2.
- q Site should follow-up directly with the participant via phone to remind the participant.
- r Participants to return all study drug dispensed at previous visits and only use the newly dispensed study drug. Participants should be reminded not to take study drug on the days of a study visit until instructed by the study site.

NOTE: All laboratory assessments are to be performed in central laboratories, except for tests completed using dipsticks and drug and alcohol screen tests which will be done locally. Laboratory kits used locally will be provided by the central laboratory.

NOTE: Where the values for the following investigations are outside the usual range for a participant during screening, based on their medical history, retesting may be undertaken on one occasion without requiring a re-screen: Blood pressure, eGFR, spot urine for ACR, ALT, AST, bilirubin, and serum potassium.

Abbreviations: ABPM = ambulatory blood pressure monitoring; ACR = albumin to creatinine ratio; AEs = adverse events; ALT = alanine aminotransferase; AST = aspartate aminotransferase; BMI = body mass index; CKD = chronic kidney disease; CSP = clinical study protocol; DKD = diabetic kidney disease; ECG = electrocardiogram; e-Diary = electronic Diary; eGFR = estimated glomerular filtration rate; FSH = follicle stimulating hormone; fT3=free triiodothyronine; fT4=free thyroxine; h = hour, HbA1c = glycated haemoglobin; hCG = human chorionic gonadotropin; LH = luteinising hormone; **CCI**; PK = pharmacokinetic(s); SAEs = serious adverse events; TSH=thyroid stimulating hormone.

Appendix B: Interim Analysis Plan

This section stipulates definitions of analysis sets, key efficacy endpoints and statistical methods for the interim analysis.

The administrative interim analysis is planned when about 200 participants have completed their 20-week treatment. The purpose of the interim analysis is to trigger the activities related to the Phase 3 program, it will not impact the design and the conduct of FLAIR.

B.1. Analysis Sets

Analysis Set	Analysis Population	Data Period
Interim Safety	The cohort of the first 240 participants who had been randomised and took at least one dose of study medication.	Day 1 to the end of the end of Treatment Period 2 (ie, Week 20)
Interim Per Protocol	The participants in the interim Safety set who completed the first 12-week treatment, eligible to enter the second treatment period and receive the additional treatment with dapagliflozin post-Week 12. Participants should have no important protocol deviations which are identified as requiring exclusion from Per-Protocol analysis set.	Day 1 to the end of the end of Treatment Period 2 (ie, Week 20)

Note: 240 participants randomised accounts for expected drop-out to ensure approximately 200 participants complete Week 20.

B.2. Efficacy Analysis

The efficacy variable to be summarized are UACR and eGFR. The key endpoint is the UACR reduction from baseline to Week 20. It will be analysed by means of the MMRM approach as described in Section 4.9.2.1 using the Interim Per Protocol Analysis Set. The Least Squares estimate of the placebo-adjusted UACR reduction and its SE will be used to construct the decision plot. The following decision criteria and actions will be considered.

Interim Outcome	UACR reduction from baseline to Week 20	Action recommended
Go	Estimate in Green Zone	Move forward to Phase 3 ID, trigger further investment and activities to enable start of Phase 3
No Action	GO criteria not met	No trigger of further investment and activities to enable start of future studies.

[figure not shown]
The GO thresholds in terms of the placebo-adjusted UACR reduction are calculated as

$$GO = \max(e^{(\log(LRV)+q_{0.8}\sigma)} * 100 - 100, e^{(\log(TV)-q_{0.9}\sigma)} * 100 - 100) \%$$

Where

σ = the standard error of the estimate,
 $q_{0.8} = \Phi^{-1}(0.8)$ ie, the 0.8-level quantile of the normal distribution,
 $q_{0.9} = \Phi^{-1}(0.9)$ ie, the 0.9-level quantile of the normal distribution,
 TV = 0.357 representing a Target Value (TV) of 30%,
 LRV = 0.223 representing a Lower Reference Value (LRV) of 20%.

A decision plot will be created for UACR reduction for the placebo-adjusted estimates of AZD5718 **CC1**, **CC1** and **CC1** mg at week 20. A schematic example of a decision plot for UACR reduction at week 20 for the AZD5718 is illustrated below.

Abbreviations: LRV = Lower Reference Value; TV = Target Value; UACR = urine albumin to creatinine ratio.

Initiation of future studies requires at least one dose to have GO for the placebo-adjusted UACR reduction at week 20 and the response of the other doses pointing in the right direction.

Reference:

Paul Frewer, Pat Mitchell Claire Watkins and James Matcham, Decision-making in early clinical drug development, Pharmaceutical Statistics 2016, 15 255–263

B.3. Safety Analysis

Safety analysis will be based on the Interim Safety Analysis set. Selected safety outputs will be presented by treatment group and overall.

The number, percentage and percentage per participant exposure year (PEY) of participants reporting TEAEs in each treatment group will be tabulated by SOC and PT, by SOC. A summary of adverse events in any category will be presented by treatment. The incidence of common ($\geq 5\%$ of participants in any treatment group) treatment-emergent AEs, common treatment-emergent serious AEs, and AEs leading to discontinuation of study medication will be summarized by SOC, PT and treatment group, sorted in decreasing overall (across treatments) frequency. Moreover, treatment-emergent AEs leading to hospitalization will also be presented.

Listings will be presented of participants with SAEs, AEs leading to discontinuation, and participants who died. A listing will be presented of participants with AEs, detailing whether these are SAEs, AEs leading to discontinuation, or resulting in death.

Summary statistics of laboratory data (as described in Section 4.10.4) will be presented. Participants with laboratory values which are highlighted as abnormal will be listed. Summary statistics of vital signs data may be collected.

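### The interim GO formula in SAP Appendix B.2 takes logs of constants that are already logs, so it cannot return the 20% and 30% UACR reductions it is built on

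*SAP*

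**What the plan says.** SAP Appendix B.2 makes the placebo-adjusted UACR change at Week 20 the key interim endpoint, analysed by the MMRM of Section 4.9.2.1 on the Interim Per Protocol set. "The Least Squares estimate of the placebo-adjusted UACR reduction and its SE will be used to construct the decision plot". An estimate in the green zone is a GO, which recommends moving towards Phase 3; otherwise no action follows. Starting future studies needs a GO for at least one dose, with the other doses supportive in direction.

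The bar is introduced by "The GO thresholds in terms of the placebo-adjusted UACR reduction are calculated as" and is then printed as

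`GO = max( exp(log(LRV) + q0.8*SE)*100 - 100, exp(log(TV) - q0.9*SE)*100 - 100 ) %`

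Here SE is the standard error of the estimate, and q0.8 and q0.9 are standard normal quantiles. The constants are "TV = 0.357 representing a Target Value (TV) of 30" per cent and "LRV = 0.223 representing a Lower Reference Value (LRV) of 20" per cent. No other section gives a different definition or a worked threshold. The direction of the ratio and the sign of the plotted estimate are not stated in the text available to this review. The SAP says that "A schematic example of a decision plot for UACR reduction at week 20 for the AZD5718 is illustrated below", but that figure is not available here.

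**The concern.** The formula has the form of a two-criterion rule. The estimate must exceed the lower reference value by 0.84 standard errors, and must not fall more than 1.28 standard errors below the target value. A rule of this kind has a simple check: as SE tends to zero, each term must return its own reference value. The printed terms do not.

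The constants are natural logs of ratios, with the minus sign dropped. The formula treats them as ratios and logs them again, so its output is not a percentage reduction.

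This is the plan's only numerical GO threshold, and its use lies in having been fixed in advance in a form that someone else can reproduce. As printed, a second programmer could not reproduce the intended bar without first deciding what the SAP meant.

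**Working it through.** **Inputs from SAP Appendix B.2.** LRV = 0.223 (for 20%), TV = 0.357 (for 30%), q0.8 = 0.8416, q0.9 = 1.2816. The log is taken as natural, because the back-transform uses e and SAP Section 4.13 names the natural log scale.

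**1. What the constants are.** -ln(1 - 0.20) = 0.2231 and -ln(1 - 0.30) = 0.3567. Both match to the digits printed.

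**2. Check at SE = 0.** The first two columns are the LRV and TV terms.

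| Reading | LRV | TV | Comment |
|---|---|---|---|
| As printed, natural log | -77.7% | -64.3% | 0.223*100 - 100; 0.357*100 - 100 |
| Base-10 log | -47.9% | -36.1% | not 20 and 30 |
| log(1 + x) | +22.3% | +35.7% | not 20 and 30 |
| Outer log dropped | +25.0% | +42.9% | placebo/active ratio minus 1 |
| Ratios 0.80 and 0.70 inside the printed log | -20.0% | -30.0% | needs different constants; see step 3 |
| Log dropped, constants negated | -20.0% | -30.0% | needs different constants |

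No reading that keeps the printed constants returns 20% and 30%.

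**3. Which reading fits the printed signs and max().** With ratios 0.80 and 0.70 inside the log, the plus and minus signs and the max() point the wrong way for a reduction: the bar at SE 0.12 becomes -11.5%. The printed structure works only if log(LRV) = 0.223 and log(TV) = 0.357, that is, placebo/active ratios of e^0.223 = 1.250 and e^0.357 = 1.429. These do correspond to reductions of 1 - 1/1.250 = 20% and 1 - 1/1.429 = 30%. The output is then on the placebo/active minus 1 scale, which is still not a percentage reduction.

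**4. Which criterion binds.** The two terms are equal at:
- intended: (0.357 - 0.223) / (0.8416 + 1.2816) = 0.134 / 2.1232 = 0.063
- printed: ln(0.357/0.223) / 2.1232 = 0.4706 / 2.1232 = 0.222

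The TV term binds below the switch point and the LRV term above it. Between SE 0.063 and 0.222, the printed formula applies the wrong criterion.

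**5. Size at a plausible interim SE (assumed).** The planning SD is redacted, so I assume 0.75 on the log scale, range 0.6 to 1.0. SAP B.1 notes that "240 participants randomised accounts for expected drop-out to ensure approximately 200 participants complete Week 20", which is 200/4 = 50 per arm. With SE = SD*sqrt(2/50), SE = 0.15 (0.12 to 0.20).

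| SE | Printed LRV term | Printed TV term | Printed bar | Intended bar (reduction) |
|---|---|---|---|---|
| 0.12 | -75.3% | -69.4% | -69.4% | 27.7% |
| 0.15 | -74.7% | -70.5% | -70.5% | 29.5% |
| 0.20 | -73.6% | -72.4% | -72.4% | 32.4% |

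The intended bar is 100*[1 - exp(-max(0.223 + 0.8416*SE, 0.357 - 1.2816*SE))]. At SE 0.15 this is 100*(1 - e^-0.349) = 29.5%. SAP Section 4.12 gives a different count: "An administrative interim analysis will be performed for this study when approximately 211 participants have reached Week 20". With 211/4 = 52.75 per arm, the intended bar is 29.2% (27.5% to 32.1%). It passes the 30% target itself once SE exceeds 0.134/0.8416 = 0.159.

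**6. Per-dose probability of GO if the printed bar were applied literally.** Let d = -ln(1 - true reduction); the estimate is taken as normal on the log scale. The printed bar is read in each of the two possible directions.

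| Rule | True effect | SE 0.15 | Across SE 0.12 to 0.20 |
|---|---|---|---|
| Printed, GO if % reduction is at or above -70.5 | none | 1 - Phi[(-ln 1.705 - 0)/0.15] = 0.9998 | above 0.99 throughout |
| Printed, GO if active/placebo change is at or below -70.5% | 40% reduction | 1 - Phi[(-ln 0.295 - 0.511)/0.15] = 1.1e-6 | below 0.0001 throughout |
| Intended | none | 1 - Phi[0.349/0.15] = 0.010 | 0.003 to 0.025 |
| Intended | 40% reduction | 1 - Phi[(0.349 - 0.511)/0.15] = 0.86 | 0.94 to 0.72 |

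**The case against.** The strongest reply accepts the algebra and disputes its weight.

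- **The intent can be recovered.** The 20% and 30% stand beside the constants, so a statistician can work out the rule. This is true, and it is why mislabelled constants are the likeliest explanation. But two repairs are possible, on different output scales, and the text does not choose between them.
- **The rule is spent and internal.** SAP version 3.0 postdates the interim. The rule governed sponsor investment and set no alpha, stopping boundary or participant-level action. This also stands, and it limits the remedy to a clarification. Version 3.0 nevertheless still carries the formula as the record of the rule.
- **Literal programming would be noticed.** A bar near -70% would probably be queried, and the two extreme probabilities in step 6 come from opposite sign conventions. They show that the printed rule is unusable either way; they do not describe what happened. They are also per dose, whereas the full decision looks across doses.
- **The SE range is assumed.** The SD is redacted, and the Interim Per Protocol set may be smaller than 50 per arm. This is fair for steps 5 and 6. Steps 1 to 4 need neither figure.
- **The missing plot may settle scale and direction.** It may, but it cannot undo the second log.

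**Conclusion.** The concern holds. As printed, the threshold is wrong. At SE = 0 it returns -77.7% and -64.3% where it should return 20% and 30%, and the binding criterion changes at SE 0.222 instead of 0.063. These figures rest only on numbers in SAP Appendix B.2 and on the natural log.

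The comparison of a -70.5% bar (-69.4% to -72.4%) with an intended 29.5% reduction (27.7% to 32.4%) rests on the assumed SD of 0.6 to 1.0 and 50 completers per arm. The probabilities of GO rest on these too, and on normality of the estimate.

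The documents do not show which formula was programmed, so they do not show that any GO or No Action call was wrong. The final efficacy analysis does not use this formula. SAP Section 4.12.1 states: "Following the results observed at the interim analysis, it was confirmed by sponsor to terminate the study due to lack of efficacy". It does not mention the threshold, and I draw no link between the two. The point should be fixed because this is the only numerical statement of the interim decision rule.

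**What to change.** Use one of two equivalent corrections, with SE on the natural-log scale.

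1. **Replace the formula.** GO if 100*(1 - active/placebo geometric mean ratio) is at least 100*[1 - exp(-max(0.223 + q0.8*SE, 0.357 - q0.9*SE))]. At SE = 0 the two terms return 20% and 30%.
2. **Keep the formula and relabel the constants.** State log(LRV) = 0.223 and log(TV) = 0.357, the logs of placebo/active ratios 1.25 and 1.429, and say that the estimate is plotted on the same placebo/active minus 1 scale.

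Then check which version the interim program used for the decision plot. Restate GO or No Action by dose only if it differed from the corrected rule.

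The cost is a short clarifying note to the SAP (the interim is past, so no re-planning is involved) and one check of code. No new data are needed.
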